3.2 Analysis Populations

3.2.1 *Safety Population*

The Safety Population is defined as all randomized subjects who receive at least 1 dose of study drug.

3.2.2 *Intent-to-Treat Population*

The Intent-to-Treat (ITT) Population is defined as all subjects who have at least 1 dose of study drug and 1 efficacy measurement.

3.3 Subject Data and Study Conduct

3.3.1 *Subject Disposition and Analysis Populations*

The number of subjects who are randomized and treated in the study and the number and percentage of subjects who complete the study will be presented. Counts and percentages of subjects who is withdrawn or discontinue from the study, and the reason for withdrawal or discontinuation, will also be summarized based on all randomized subjects.

Counts and percentage of subjects in each analysis population will be tabulated by treatment sequence and in total. Reasons for exclusion from each analysis will also be summarized.

3.3.2 *Protocol Deviations*

Counts and percentages of subjects with protocol deviations by deviation category will be summarized by treatment sequence and in total based on the Safety Population.

3.3.3 *Demographic and Baseline Characteristics*

The following demographic and baseline characteristics will be summarized:

- Age (years) and age categories (<65 years, ≥65 years)
- Sex
- Childbearing potential
- Race
- Ethnicity
- Height (cm)
- Weight (kg)
- Body mass index (BMI) (kg/m²)

Demographic and baseline characteristics will be summarized with descriptive statistics or counts and percentages of subjects as appropriate by treatment sequence and in total based on the Safety Population.

3.3.4 *Medical History*

Medical history will be coded to system organ class and preferred term using the Medical Dictionary for Regulatory Activities (MedDRA) version 24.0. Counts and percentages of subjects with medical history by system organ class and preferred term will be summarized by treatment sequence and in total based on the Safety Population.

3.3.5 *Concomitant Medications*

Concomitant medications will be coded to anatomical therapeutic chemical (ATC) class and preferred term using the WHO Drug Dictionary version Mar 2021G B3.

Prior medications are defined as those occurring prior to the date of first dose of study drug. Concomitant medications refer to those on or after first dose of study drug. Prior medications that are ongoing will qualify as concomitant. Medications that were started prior to the first dose of study drug and were ongoing as of the date of first dose of study drug will be considered both prior and concomitant.

Counts and percentages of subjects taking prior and concomitant medications by ATC class and preferred term will be summarized by treatment sequence and in total based on the Safety Population.

3.3.6 *Study Drug Exposure and Compliance*

Study drug exposure will be summarized by the total number of tablets taken based on the Safety Population. Compliance (%) will be calculated based on (the total number of tablets taken/expected number of tablets taken) *100 per dosing.

Subjects who take 100% of study drug per protocol in accordance with their treatment will be considered treatment-compliant.

3.4 Efficacy Assessment

Efficacy assessment will be summarized on the ITT Population.

The primary exploratory efficacy endpoints will include the following:

Assessment of symptoms

- Global Impression Visual Analog Scale
- Clinical Global Impression (CGI)-Impairment Severity Scale

- CGI-Improvement Scale
- Alcohol Toxicity Symptom Scale (thirsty or dehydrated, more tired than usual, headache, nausea, vomiting, weak, difficulty concentrating, sensitive to light and sound, sweating, anxious, depressed, trembling or shaking)

Assessment of signs

[figure not shown]
- Objective flushing and ocular redness scales (via digital photography)
- Proprioception tests (Romberg Test [time of up to 60 seconds], One Leg Stand Test [time of up to 60 seconds], Straight-Line Heel-to-Toe Test [up to 100 steps]).

Assessment of ADX-629 pharmacodynamic activity

- PD markers: HNE, acetaldehyde, malondialdehyde-acetaldehyde adduct (MAA), and MDA plasma concentrations;
- Plasma cytokine concentrations including, but not limited to, interferon gamma, IL-1b, IL-10, IL-12, and IL-17

Factors:

- Timepoint
- Baseline
- BAC
- Number of bodyweight-standardized drinks consumed
- Emesis volume
- Emesis 8-12 hours after first drink (binary)

3.5 Safety Assessment

Safety data will be summarized by treatment sequence and in total based on the Safety Population.

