- Day 2: 1 dose of study drug will be administered at approximately 8 am, and symptom and sign assessments (including the CGI-Improvement Scale) will be completed at approximately 7 am, 10 am, and 1 pm. Subjects will be discharged from the study site after completion of study procedures (approximately 12 hours after the last dose of study drug). Prior to discharge, vital signs will be measured. Subjects will have to achieve a BAC of 0.00 g/100 mL as measured by a breathalyzer before discharge.
- A follow-up telephone call will occur 3 days (± 1 day) after completion of Treatment Period 2.

For subjects who are withdrawn from the study prior to completion, study procedures will be performed at an Early Termination Visit.

There will be a 14-day (± 2 days) washout period between the last dose of study drug in Treatment Period 1 and the first dose of study drug in Treatment Period 2. Subjects will need to refrain from drinking alcohol during the washout period.

2.2.2 *Randomization and Blinding*

Subjects will be randomized to 1 of 2 treatment sequences (AB or BA) on Day 1 of Treatment Period 1.

- Treatment A: 3 oral doses of ADX-629 600 mg (2×300 mg) oral tablets; and
- Treatment B: 3 oral doses of matching placebo.

Subjects, Investigators, and study site personnel (including the Sponsor/designee) involved in the administration and assessment of the study drug will be blinded to the subject treatment assignments throughout the study.

2.2.3 *Study Drug*

All subjects will receive 3 doses of ADX-629 600 mg (2×300 mg) oral tablets and 3 doses of matching placebo. The study drug will be administered twice on Day 1, the first dose prior to the commencement of the standardized ethanol consumption, and once on the day following ethanol consumption (Day 2). No dose interruptions or reductions will be permitted.

2.2.4 *Sample Size Determination*

Approximately 30 subjects are expected to be enrolled in the study. The sample size is not based on statistical considerations and is not formally powered as all endpoints are exploratory in nature.

2.3 *Study Endpoints*

As this study is not formally powered and there are no adjustments for multiplicity, and since the interaction between ethanol and ADX-629 has not been previously assessed, all efficacy endpoints are exploratory.

2.3.1 *Primary Exploratory Efficacy Endpoints*

The primary exploratory efficacy endpoints include the following:

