3.1.3 Definition of Baseline

Baseline for safety assessments is defined as the last measurement prior to the first dose of study drug.

Baseline for efficacy assessments is defined as the last measurement prior to the first dose of study drug for each study period.

3.1.4 *Summary Statistics*

In general, categorical variables will be summarized by the count and percentage of subjects. Continuous variables will be summarized by the number of non-missing observations, mean, standard deviation, median, minimum, and maximum values.

3.1.5 *Handling of Dropouts and Missing Data*

Dates for AEs and concomitant medications will be printed in a format of DDMMYY YYYY. In cases of incomplete dates for AE and concomitant medications, no imputation of start/end dates or times will be performed. If the partial AE onset date information does not indicate that the event started prior to or after the treatment, the event will be classified as treatment-emergent.

If a medication date is missing or partially missing and it cannot be determined whether it was taken prior or concomitantly, it will be considered a concomitant medication.

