3.5.1 Adverse Events (AEs)

All AEs will be coded to system organ class and preferred term using MedDRA version 24.0. Treatment-emergent adverse events (TEAEs) are defined as AEs that start after the first dose of study drug.

An overview of AEs will be provided including counts and percentages of subjects (and event counts) with the following:

[figure not shown]
- Any AEs
- Any AEs related to COVID-19
- Any TEAEs (overall and by maximum severity)
- Any study drug related TEAEs (overall and by maximum severity)
- Any serious AEs (SAEs)
- Any treatment-emergent serious AEs (TESAEs)
- Any TEAEs leading to discontinuation of study
- Any AEs leading to death

Counts and percentages of subjects (and event counts) will also be presented by system organ class and preferred term for each of the categories in the overview.

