3.5.2 Clinical Laboratory Tests

Clinical laboratory assessments will include clinical chemistry, hematology, and urinalysis.

Continuous laboratory variables will be summarized in terms of observed values and the change from Baseline at each visit. Categorical laboratory variables will be summarized at each visit with counts and percentages of subjects.

A blood sample for lipid panel evaluation will be collected after fasting at Screening and on Day 2 of both treatment periods. Observed values and change from Baseline at each scheduled visit will be summarized.

3.5.3 *Vital Signs*

Vital signs will include blood pressure, heart rate, respiratory rate, temperature, and oxygen saturation.

Observed values and change from Baseline at each scheduled visit and timepoints will be summarized.

3.5.4 *Blood Alcohol Concentration*

Ethanol will be administered in a standardized oral solution to reach a target BAC of 0.14 g/100 mL following the first dose of study drug on Day 1.

A confirmatory blood ethanol test will be obtained on Day 1 of both treatment periods after the start of ethanol consumption but prior to the subject's final drink and associated 45-minute breathalyzer test.

All the data collected will be listed.

3.5.5 *Electrocardiograms*

Each continuous variable - heart rate (bpm), PR interval (msec), QRS duration (msec), QT interval (msec), QTcF (msec), RR interval (msec) - will be summarized in terms of observed values and changes from Baseline at each visit.

Overall interpretation (normal/ abnormal and not clinically significant/ abnormal and clinically significant) will be summarized along with the proportion of subjects with abnormal QTcF intervals in the categories below will be provided.

- Absolute QTcF interval >450 msec
- Change from baseline QTcF interval increase >30 msec

All the data collected will be listed.

3.5.6 *Physical Examinations*

A complete physical examination will be performed at Screening (and the Early Termination Visit, if applicable) and will consist of general appearance, skin, head, eyes, ears, mouth, oropharynx, neck, heart, lungs, abdomen, extremities, and neuromuscular system.

Counts and percentages of subjects with physical examination abnormalities will be summarized at each visit.

All the data collected will be listed.

3.5.7 *Other Safety Assessments*

Drug and alcohol screen, SARS-CoV-2 RNA, FSH test, Peth blood test, pregnancy testing, fibroscan, AUDIT test and CAGE questionnaire will be listed.

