6 PROGRAMMING SPECIFICATIONS

Analyses will be performed using SAS® version 9.3 or higher. All available data will be presented in subject data listings which will be sorted by subject and visit date as applicable. Detailed Programming Specifications will be provided in a separate document.

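### Adverse event tables by treatment sequence pool drug and placebo periods, so they cannot show ADX-629 against placebo

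*SAP*

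**What the plan says.** SAP 3.5 sets one column rule for all safety output: "Safety data will be summarized by treatment sequence and in total based on the Safety Population". SAP 3.5.1 then describes an AE overview of subject and event counts, and continues: "Counts and percentages of subjects (and event counts) will also be presented by system organ class and preferred term". It names no visit, period or treatment received.

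Treatment emergence is defined once: "Treatment-emergent adverse events (TEAEs) are defined as AEs that start after the first dose of study drug". The only AE date rule, in SAP 3.1.5, begins "If the partial AE onset date information does not indicate that the event started prior to or after the treatment" and settles only whether such an event counts as treatment-emergent.

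On the design, SAP 2.2.3 states "All subjects will receive 3 doses of ADX-629 600 mg" and that the same subjects also receive three doses of placebo. Protocol 8 makes the safety and tolerability of ADX-629 the primary safety endpoint, with AEs listed first. Protocol 9.2.3 limits the safety analysis to listings, descriptive summaries and shift tables. Protocol 8.1 collects AEs from consent to the end of participation, which spans both treatment periods and the washout.

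**The concern.** In a two-period crossover, sequence is the order of treatment. Sequence columns suit demographics and disposition, where SAP 3.3 uses them. For AEs, the AB column holds drug events from Period 1 and placebo events from Period 2, and the BA column holds the reverse. The total column adds them together. No column is ADX-629 and no column is placebo.

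Other elements of the plan do not separate the treatments:

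- **Treatment-emergent definition.** Whether first dose means the first in the trial or the first in each period, post-dose events of both periods fall in the same sequence column. SAP 3.5.4 uses similar words ("following the first dose of study drug on Day 1") for something that happens in each period, so the anchor could be clearer, but clarifying it would not cure the pooling.
- **Study-drug-related rows.** Protocol 4.3 uses study drug for ADX-629 or placebo, and the investigator's yes/no rating is made blinded.
- **Protocol 9.2.3 and SAP 5.** The first sets no treatment column. The second lists only a change of analysis population.

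Safety is descriptive only, so the AE tables are the planned summary of AEs. If they cannot distinguish drug from placebo, the treatment comparison is left to hand attribution from listings, by rules not fixed in advance.

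**Working it through.** The plan gives no AE rate under ethanol and no figure to reproduce, so this is a check of what the described table can show.

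**Inputs**
- About 30 subjects (SAP 2.2.4); 15 per sequence is assumed, because the readable text gives no allocation ratio.
- Per-period risk of at least one AE: pA on ADX-629 and pB on placebo. All values are assumed except one illustration from Protocol 1.1.2: 9.4% on ADX-629 and 19.1% on placebo in Phase 1 healthy volunteers.

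**1. No period effect, carry-over or dropout; independent periods**

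AB = 1 − (1 − pA)(1 − pB) and BA = 1 − (1 − pB)(1 − pA). The two are equal, and symmetric in pA and pB.

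| pB (placebo) | pA (ADX-629) | AB | BA |
|---|---|---|---|
| 20% | 20% | 36% | 36% |
| 20% | 40% | 1 − 0.6 × 0.8 = 52% | 52% |
| 40% | 20% | 1 − 0.8 × 0.6 = 52% | 52% |
| 20% | 60% | 68% | 68% |
| 50% | 50% / 70% / 90% | 75% / 85% / 95% | 75% / 85% / 95% |
| 19.1% | 9.4% | 1 − 0.906 × 0.809 = 26.7% | 26.7% |

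Event counts behave the same way. Means of 0.4 on drug and 0.2 on placebo give 0.6 per subject, or 9 events per 15 subjects, in each column. Within-subject correlation (logit random intercept, SD 1 or 2, marginal risks held at 20% and 40%) moves the 52% to 49.1% or 45.3%, still equal in both columns.

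**2. Conditions relaxed, pB = 20% and pA = 40% in Period 1 (true difference +20 points)**

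- Period 2 odds doubled: pB becomes 33.3% and pA 57.1%. AB = 1 − 0.6 × 0.6667 = 60.0%; BA = 1 − 0.8 × 0.4286 = 65.7%; AB − BA = −5.7 points.
- Period 2 odds halved: pB becomes 11.1% and pA 25%. AB = 46.7%; BA = 40.0%; +6.7 points.
- A fraction d leaving each sequence after Period 1: AB = 1 − (1 − pA)(1 − (1 − d)pB), BA = 1 − (1 − pB)(1 − (1 − d)pA). For d = 10%, 50.8% − 48.8% = +2.0; for d = 20%, 49.6% − 45.6% = +4.0.

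By treatment received, with balanced sequences, the same data show (40 + 57.1)/2 = 48.6% against (20 + 33.3)/2 = 26.7%, +21.9 points, with odds doubled. With odds halved they show 32.5% against 15.6%, +16.9 points.

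**3. An AE that occurs only on drug, pA = 10%**

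Under the conditions of step 1, AB and BA are both 10.0%. With Period 2 odds doubled, AB is 10.0% and BA 18.2%. With 20% dropout, AB is 10.0% and BA 8.0%.

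**4. How often the table ranks its columns one way (exact binomial, 15 per sequence, pB = 20%, conditions of step 1)**

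| pA | AB column above BA | By-treatment table: ADX-629 above placebo |
|---|---|---|
| 20% | 42.5% | 43.6% |
| 40% | 42.8% | 94.3% |
| 60% | 42.2% | 99.9% |

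The last column treats 30 and 30 as independent binomials, although they are the same subjects. At pA = 40%, allowing for pairing (random intercept SD 1 or 2) gives about 96–98% instead of 94.3%. With Period 2 odds doubled at 20% against 40%, BA exceeds AB in 55.5% of trials and AB exceeds BA in 30.3%.

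**The case against.** The strongest reply is that the readable SAP is not the whole specification. SAP 6 says "Detailed Programming Specifications will be provided in a separate document", a figure within SAP 3.5.1 is missing from the text, and Appendix A shows only its heading. A split by treatment could sit in any of these. That limit stands, and the claim is confined to the readable SAP. But the text states a column rule that, if followed, gives the wrong tables.

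Sequence could also be a slip for treatment. The Protocol synopsis speaks of comparing the two treatment sequences and then specifies a model with treatment effects. Against this, that model lists sequence as a separate term, and SAP 3.3 uses treatment sequence in its ordinary sense for demographics.

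The data are not lost. SAP 6 lists all available data by subject, dosing is supervised in an inpatient unit, and onset can usually be matched to a period. The study is exploratory and unpowered, and no readable decision rule depends on these tables. All this limits the seriousness, but attribution from listings would not be pre-specified.

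Laboratory values, vital signs and continuous ECG values are summarized by visit, so sequence by period identifies the treatment if visits are kept separate by period. The point does not extend to them. For the QTcF categories, SAP 3.5.5 says only "proportion of subjects with abnormal QTcF intervals in the categories below will be provided", without naming a visit or period. The neighbouring by-visit layout may be intended, so that part is secondary.

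**Conclusion.** The concern holds for the AE tables as the readable SAP describes them. Without a period effect, carry-over or dropout, the two sequence columns have the same expected content whatever ADX-629 does, and exchanging the drug and placebo risks leaves the table unchanged. This equality needs no particular AE rate, and it held under the within-subject correlation examined. When those conditions fail, the columns differ because of period or dropout, and the difference can take either sign: −5.7 to +6.7 points in the cases examined, against a true Period 1 difference of +20. Those sizes rest on assumed rates and 15 subjects per sequence.

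This should be fixed. It leaves the primary safety endpoint without an AE summary by treatment, but it is a reporting defect that costs little to repair.

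**What to change.** In SAP 3.5 and 3.5.1:

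- Present all AE tables by treatment received (ADX-629, placebo) and in total. Use as denominator the subjects who received at least one dose of that treatment.
- State the attribution rule before unblinding. One option is the treatment most recently dosed before onset, with washout-onset events either assigned to the Period 1 treatment or shown in a separate row.
- Say where an event goes when its partial onset date does not identify the period, since SAP 3.1.5 allows no date imputation. A row for treatment not determinable would serve.
- Say how an AE that starts in Period 1 and worsens in Period 2 is counted, for example as a new event under the Period 2 treatment from the date of worsening.
- In SAP 3.5.5, give the QTcF category counts (above 450 msec; increase above 30 msec) by treatment as well.

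The exact rules for washout, indeterminate dates and worsening are a choice; what matters is that they are written down. If the programming specifications already contain such rules, move them into the SAP. The cost is a few sentences and new AE and QTcF table shells. AE onset and dosing dates are already collected, and no more subjects are needed.

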3.5.1 Adverse Events (AEs)

All AEs will be coded to system organ class and preferred term using MedDRA version 24.0. Treatment-emergent adverse events (TEAEs) are defined as AEs that start after the first dose of study drug.

An overview of AEs will be provided including counts and percentages of subjects (and event counts) with the following:

[figure not shown]
- Any AEs
- Any AEs related to COVID-19
- Any TEAEs (overall and by maximum severity)
- Any study drug related TEAEs (overall and by maximum severity)
- Any serious AEs (SAEs)
- Any treatment-emergent serious AEs (TESAEs)
- Any TEAEs leading to discontinuation of study
- Any AEs leading to death

Counts and percentages of subjects (and event counts) will also be presented by system organ class and preferred term for each of the categories in the overview.

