- Day 1: 1 dose of study drug will be administered at approximately 4:30 pm followed by standardized ethanol consumption as outlined in the manual, and then 1 dose of study drug will be administered at approximately 7 pm followed by continued standardized ethanol consumption to reach a target blood alcohol concentration (BAC) of 0.14 g/100 mL, measured via breathalyzer. For more details on the breathalyzer measurements, refer to the Study Procedures Manual. Symptom and sign assessments (with the exception of the CGI-Improvement Scale) will be evaluated and should be completed as soon as practical after target BAC is reached. Study procedures will be reviewed for randomized subjects, and, based on the emerging data, the standardized ethanol solution and/or BAC testing methods may be modified as needed to ensure target BAC is reached within a 4-hour window for the remaining subjects; and

Note: Subjects will be observed for safety during the treatment periods by study site personnel who will be present to assist subjects at all times; there will be a minimum

requirement of at least 2 study site personnel to assist subjects during their assessments. Safety measures will be in place to prevent falling.

Note: Ethanol will be administered in a standardized oral solution. For more details on the consumption guidelines, refer to the Study Procedures Manual.

- Day 2: 1 dose of study drug will be administered at approximately 8 am, and symptom and sign assessments (including the CGI-Improvement Scale) will be completed at approximately 7 am, 10 am, and 1 pm. Subjects will be discharged from the study site after completion of study procedures (approximately 12 hours after the last dose of study drug). Prior to discharge, vital signs will be measured. Subjects will have to achieve a BAC of 0.00 g/100 mL as measured by a breathalyzer before discharge.
- A follow-up telephone call will occur 3 days (± 1 day) after completion of Treatment Period 2.

For subjects who are withdrawn from the study prior to completion, study procedures will be performed at an Early Termination Visit.

There will be at least a 14-day washout period between the last dose of study drug in Treatment Period 1 and the first dose of study drug in Treatment Period 2. Subjects will need to refrain from drinking alcohol during the washout period.

An individual subject's participation in the study is estimated to be approximately 41 days.

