8.1 Adverse Events

An AE is defined as any untoward medical occurrence in a clinical investigation subject administered a pharmaceutical product, which does not necessarily have a causal relationship with this treatment. An AE can therefore be any unfavorable and/or unintended sign (including an abnormal laboratory finding), symptom, or disease temporally associated with the use of an investigational medicinal product, whether or not related to the investigational medicinal product. All AEs, including observed or volunteered problems, complaints, or symptoms, are to be recorded on the appropriate eCRF.

AEs, which include clinical laboratory test variables, will be monitored and documented from the time of informed consent until study participation is complete. SAEs occurring from the time of informed consent until 30 days following the last administration of study drug will be monitored and documented. Subjects should be instructed to report any AE that they experience to the Investigator, whether or not they think the event is due to study treatment. Beginning at Screening, Investigators should make an assessment for AEs at each visit and record the event on the appropriate AE eCRF.

Wherever possible, a specific disease or syndrome rather than individual associated signs and symptoms should be identified by the Investigator and recorded on the eCRF. However, if an observed or reported sign or symptom is not considered a component of a specific disease or syndrome by the Investigator, it should be recorded as a separate AE on the eCRF. Additionally, the condition that led to a medical or surgical procedure (eg, surgery, endoscopy, tooth extraction, or transfusion) should be recorded as an AE, not the procedure itself.

Any medical condition already present at Screening should be recorded as medical history and not be reported as an AE unless the medical condition or signs or symptoms present at baseline changes in severity, frequency, or seriousness at any time during the study. In this case, it should be reported as an AE.

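### The TEAE definition has one study-level start, no period or treatment assignment and no worsening clause, so the planned AE tables of this crossover cannot separate ADX-629 from placebo

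*SAP*

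**What the plan says.** The definition in SAP 3.5.1 is a single sentence: "Treatment-emergent adverse events (TEAEs) are defined as AEs that start after the first dose of study drug". It sets no end, does not refer to a period or to the treatment being taken, and does not mention an event that starts earlier and then gets worse.

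The neighbouring text supports a whole-study reading. SAP 3.1.3 says "Baseline for safety assessments is defined as the last measurement prior to the first dose of study drug", while the efficacy counterpart goes on to name the period: "Baseline for efficacy assessments is defined as the last measurement prior to the first dose of study drug for each study period". SAP 3.1.1 counts analysis days from one first dose. SAP 3.5 tabulates safety by sequence and in total. Each subject is to receive both treatments (SAP 2.2.3), and the term study drug covers ADX-629 and placebo alike (Protocol 5.5.1).

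The schedule in Protocol 3.1 is:
- Day 1: "1 dose of study drug will be administered at approximately 4:30 pm followed by standardized ethanol consumption".
- Day 2: "1 dose of study drug will be administered at approximately 8 am", with discharge about 12 hours later.
- Between periods: "There will be at least a 14-day washout period between the last dose of study drug in Treatment Period 1" and the first dose of Period 2. SAP 2.2.1 gives 14 days ± 2 days instead.
- After Period 2: "A follow-up telephone call will occur 3 days" (± 1 day) after its completion, which is the last contact.

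Under Protocol 8.1, AEs are collected from consent to the end of participation and SAEs to 30 days after the last dose. A condition already present at Screening becomes a reportable AE if it "changes in severity, frequency, or seriousness at any time during the study".

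**The concern.** The rule suits a trial in which each subject takes one treatment. Here each subject takes two, so knowing that an event began after the first dose does not show which treatment preceded it. An AB subject's count mixes events on ADX-629, events in the washout and events on placebo, and a BA subject's count mixes the same three in the other order.

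The primary safety endpoint (Protocol 8) is the safety and tolerability of ADX-629, and safety is part of the primary objective (Protocol 2.1). No AE table planned in the SAP isolates events on ADX-629. The missing worsening clause adds a smaller gap: an event already under way at first dose cannot become treatment-emergent, however much it worsens afterwards.

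**Working it through.** The documents state no TEAE window, so there is no planned figure to reproduce. The lengths below follow from the schedule. Completion of a period is taken to be discharge.

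**1. Time within a period**
- First dose (4:30 pm, Day 1) to last dose (8 am, Day 2): 15.5 h = 15.5/24 = 0.646 day.
- First dose to discharge: 15.5 + 12 = 27.5 h = 1.146 days.

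**2. Non-serious AE follow-up if each event is credited to the most recent treatment, from the period's first dose**

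| Period | Basis | Calculation | Days |
|---|---|---|---|
| 1 | Protocol washout, at least 14 d | 0.646 + 14 | at least 14.65 |
| 1 | SAP washout, 12 to 16 d | 0.646 + 12 to 16 | 12.65 to 16.65 |
| 2 | Call 2 to 4 d after completion | 1.146 + 2 to 4 | 3.15 to 5.15 |

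If Period 2 also starts at 4:30 pm, the Period 1 lengths round up to 15.0 (protocol) and 13.0 to 17.0 (SAP). At the protocol minimum the ratio of Period 1 to Period 2 is 14.65/5.15 = 2.8 to 14.65/3.15 = 4.7. On the SAP washout it is 12.65/5.15 = 2.5 to 16.65/3.15 = 5.3.

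**3. Serious events**

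After Period 2, collection runs 0.646 + 30 = 30.65 days from the first dose. Period 1 has 14.65 days at the protocol minimum before the next treatment starts, so the imbalance is reversed.

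**4. Share of treatment-emergent time that is washout**

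For non-serious events the whole-study window is 14.65 + 3.15 to 5.15 = 17.8 to 19.8 days. Of this, 14 days are washout: 14/19.8 = 71% to 14/17.8 = 79%. With a 12- to 16-day washout the range is 12/17.8 = 67% to 16/19.8 = 81%. Washout is counted from the last dose, so its early part still has drug present. The reported mean half-lives are 3.49 to 6.83 h (Protocol 1.1.2), so 14 days (336 h) is 336/6.83 = 49 to 336/3.49 = 96 half-lives.

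**5. Effect on a treatment comparison, if one were made**

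Mean follow-up on ADX-629 is (n_AB × P1 + n_BA × P2)/30. For placebo, n_AB and n_BA change places. Take P1 = 14.65 and 30 subjects who complete both periods.
- Assumed 15/15 split: (14.65 + 3.15)/2 = 8.9 to (14.65 + 5.15)/2 = 9.9 days, the same for both treatments.
- Assumed 16/14 split: the difference is 2 × (14.65 − P2)/30, which is 2 × 9.5/30 = 0.6 to 2 × 11.5/30 = 0.8 day.

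**6. Worsening**
- *Condition present at Screening.* Protocol 8.1 makes its worsening an AE. If onset is dated to the worsening, it meets the TEAE definition.
- *AE first arising between consent and first dose.* Its start precedes dosing, so it is not a TEAE if it worsens later. Screening may open on Day -28, so this interval can last up to 28 days.
- *AE starting after dosing in Period 1 and worsening in Period 2.* It is already a TEAE, but no rule credits the worsening to the Period 2 treatment.

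**The case against.** A reader might infer that the definition itself creates unequal follow-up and biases the comparison of ADX-629 with placebo. The documents do not support that. The unequal lengths come from the visit schedule: a washout after Period 1 and a telephone call after Period 2. The definition only fails to limit or assign events. The planned tables are by sequence, and both sequences follow the same schedule, so their columns have the same planned follow-up. The SAP plans no drug-versus-placebo AE contrast that could be biased. If one were made, equal and complete sequences would balance the two treatments, and step 5 shows a modest effect for a mild imbalance.

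Nor does the short Period 2 follow-up show that drug-related events are being missed. The earliest call is 12 + 48 = 60 h after the last dose, or 60/6.83 = 9 to 60/3.49 = 17 half-lives. On exposure grounds Period 2 is covered, although that does not rule out delayed effects. It would also go too far to say that worsening on drug is missed in general. Protocol 8.1 handles conditions present at Screening, and a Period 1 TEAE that worsens later is still captured in the tables by maximum severity.

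Two further points can be made for the plan. An open-ended rule is inclusive, which is defensible in an exploratory safety study. All data are to be listed by subject and visit date, and detailed programming specifications are kept in a separate document (SAP 6), so the period of most events could be recovered.

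These arguments limit the size of the problem but do not remove it. The sequence tables avoid bias only because they make no treatment comparison, and so they cannot describe the safety of ADX-629. A listing is not a summary, and the definition of a TEAE belongs in the SAP.

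**Conclusion.** The point holds as a gap in definition and tabulation. Followed as written, the SAP counts every new event after the first Period 1 dose as treatment-emergent. About 71% to 79% of that time, for non-serious events at the protocol's minimum washout, is washout. The SAP assigns no event to ADX-629 or placebo, and it leaves out an AE that begins between consent and first dose and then worsens.

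The unequal follow-up of 14.65 days or more (12.65 to 16.65 on the SAP washout) against 3.15 to 5.15 days becomes relevant once events are attributed to treatment. It applies to non-serious events only, and it affects the treatment contrast only if the sequences are unequal or subjects drop out before Period 2. Withdrawals are foreseen and replacement is at the sponsor's discretion (Protocol 4.3), so exact balance is not assured.

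This rests on the whole-study reading of the definition, on discharge marking period completion, and on the approximate clock times. The change is worth making before database lock. The planned sequence tables are uninformative about ADX-629 rather than wrong.

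**What to change.** In SAP 3.5.1, define a TEAE per period: an AE with onset, or an increase in severity, from the first dose in that period until the first dose of the next period, or until the end of follow-up in Period 2. Assign it to the treatment received in that period.

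In SAP 3.5, tabulate TEAEs by treatment received as well as by sequence and in total. The per-period definition achieves little without this table. The denominator for each treatment should be the subjects dosed with it.

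In addition:
- Flag events with onset in the washout, so that they can be seen separately while staying in the count.
- Add a supplementary count over one common post-dose window that both periods can supply. The earliest call is about 2.5 days after the last dose (12 h + 2 days). Where to cut is debatable, so this should not replace the main count.
- State the SAE window separately, since it runs to 30 days after the last dose.
- Extend the partial-date rule in SAP 3.1.5, which defaults undecidable events to treatment-emergent but does not place them in a period.
- Reconcile the washout in Protocol 3.1 with that in SAP 2.2.1. SAP 5 does not list the difference.

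The cost is some SAP wording, one more derivation and one more table. No new data are needed.
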